2.7 REGARDING INCOMPLETE DATA COLLECTION

On any given assessment day, data may be incomplete for any number of reasons such as time constraints or equipment malfunctions. In such cases, not all participants will receive all tasks, measures, or procedures for this study. This information will be noted on checklists associated with each task and procedure and stored in the participant's file but will not constitute grounds for a separate note to file as it is an expected outcome and not a protocol violation.

3. PERSONNEL

Because the intervention is automated, clinical training should not be required for staff. A primary value of procedures such as these is that they may someday have translational potential in that they can be accomplished by non-clinically trained personnel. Thus, assessment and intervention personnel will include research assistants or students working in the lab who have been highly trained for the protocol and who have agreed to the lab's research associate integrity agreement (http://www.pitt.edu/~[name]/RA_integrity_agreement.docx)

### **Canonical Analysis Strategy**

Our canonical strategy for all aims in which outcome measures (e.g., physiology) are examined preintervention and post-intervention will as follows:

**Quality Control:** Data will be inspected visually and using our lab's standard algorithms to eliminate subjects, blocks, and trials in which data do not appear to be representative of the obtained measure, e.g., for EEG, data are eliminated when >3 channels have outlying means, standard deviations, are interpolated, or have unacceptably high levels of impedance.

**Preprocessing:** Data will be preprocessed using our lab's standard procedures which are consistent with industry standard procedures, e.g., via guidelines for psychophysiology from the Society for Psychophysiological Research. Outliers will be rescaled via windsorization.

**Data Reduction:** if more than one outcome measure of a given type (e.g., electrodes, for EEG) are employed, principal components analysis (PCA) will be used to yield aggregate indices across proposed outcome variables.

**Analysis:** Pre-intervention index values will be interacted with intervention type (mindfulness alone vs. TVS added to mindfulness) to explain variance in post-intervention index values using hierarchical regression; in the absence of an interaction, preintervention values will be regressed from post-intervention values before using intervention type as an independent variable to explain variance in post-intervention values in a residual regression analysis. The change in R^2 will be used as an effect size. Type I error will be controlled across the number of examined factors. Each type of outcome listed separately below will be interpreted as a statistically separate family for control of familywise error.

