2.5 Self-report Measures

--Pre-task

- 1) Demographic and screening questionnaire
- 2) Mindfulness attention awareness scale (Carlson & Brown, 2005)
- 3) Patient Health Questionnaire (Kroenke, Spitzer, & Williams, 2001)
- 4) Meditation experience questionnaire
- 5) Drug history questionnaire (Ventegodt & Merrick, 2003)
- 6) modified Differential Emotion Scale (Fredrickson, Tugade, Waugh, & Larkin, 2003)

--During tasks

- 1) Positive and Negative Affect Schedule (Watson, Clark, & Tellegen, 1988) will be given initially, and then after each intervention (meditation vs. meditation + TVS). This will also be given after the completion of each task (Mind in the Eyes, Global Local Task)

--Post-tasks

- 1) 5-Dimensional Altered State of Consciousness rating scale(Dittrich, 1998)

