2.6 Tasks

OUTLINE of procedures during the tasks

--Calibration (EEG, Pupil/Eye tracking, baseline GSR/EKG, vibration)

--Intervention 1: Meditation*

--Tasks 1: Global-Local Test, Mind in the Eyes

--Intervention 2: Meditation and TVS*

--Tasks 2: Global-Local Test, Mind in the Eyes

*Participant will be randomized whether they get meditation first or meditation and TVS first

All of tasks will be video recorded (calibration, intervention, tasks). The videos may be reviewed by study personnel and investigators for quality assurance, training purposes, or analysis. Physical backups are kept in locked filing cabinets and are labeled with subject identification number and date only. Electronic video or audio files will be stored on a password protected server which only study personnel

can access. Video and audio recordings will be kept indefinitely and may later be reviewed by other researchers. Participants may request destruction of video or audio recordings, or may also request not to be audio or video taped.

Physiological measurements during tasks include galvanic skin response (GSR) measured using electrodes placed on the index and middle finger, pupillary dilation indices, EKG (electrocardiography) which will be measured using three electrodes (left clavicle, right clavicle, and under the right rib), respiration (using a respiration belt), and EEG (mobile EEG monitor on head) will be collected during: 1) calibrations, 2) interventions and 3) cognitive and affective tasks. All of the stated physiological measurements will be collected except pupillary dilation indices will not be collected during interventions (meditation, meditation + TVS) because participants are encouraged to relax and are given the opportunity to close their eyes during those times.

A) Calibrations:

Calibration tasks will initially be completed for physiology collection including a vibration calibration that allows assessment of individualized vibration frequency preferences, a GSR/EKG calibration at baseline, EEG calibration at baseline and pupillary dilation calibration. During the EEG calibration, there are some images that may evoke negative emotions, which is in the introduction, and participants are encouraged to stop the calibration at any time if they feel uncomfortable with the images.

B) Interventions:

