Participants will undergo 2 blocks (randomized for order). 1) guided mindfulness meditation and 2) guided mindfulness meditation with TVS (0.1 Hz to 100 Hz) using SubPac, which is a marketed, wearable vibration technology that can deliver TVS, worn like a backpack. Participants will be wearing the SubPac (vest with vibration) the whole time but only during mindfulness with meditation, will the vest vibrate at various frequencies. The intensity of stimuli can vary from barely detectable through somewhat uncomfortable, but will not be painful. Similar vibratory stimuli have been standardly used in [name]'s lab. The intensity of the vibration will be adjusted to the subjects' comfort. Each of the interventions will be have a 12 minuted guided mindfulness meditation, with or without vibration coming out of the vest. They are given the choice to either sit in a desk chair or in a lounge chair, both in the same room. We advise them to concentrate to the meditation and the feelings in their body.

C) Cognitive and affective tasks:

These tasks are standard for our emotion/cognitive research lab.

1. Global-local visual processing task (Fredrickson & Branigan, 2005)

-- In general, images contain both local and global features. This task determines which attention is first directed, either at the local features (details, parts) or global features (the whole)

-- There will be a letter "T" made up of 4 smaller letter "T's". The smaller T's and the large "T" are incongruent in its orientation. The global feature of the letter "T" (the whole) will be of a particular orientation (up, down, left, right) and the local features (details, parts, in this case the 4 smaller letter "T's") will be of a different orientation (up, down, left, right). Participants will have to choose an answer by looking at the letter "T". There is no right answer, and the participant has the choose between 1) a letter "T" with congruent 4 smaller "T's" in the orientation of the global features (the whole) or 2) A letter "T" with congruent 4 smaller "T's" in the orientation of the local features (details, parts).

2. Reading the Mind in the Eyes test (Baron-Cohen, Wheelwright, Hill, Raste, & Plumb, 2001)

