### **Primary Outcome Measures**

### **1.Positive Affect Score from The Positive and Negative Affect Schedule**

The Positive Affect Score will be obtained after mindfulness meditation alone and after mindfulness meditation with TVS intervention. The Positive Affect Score will add the score on items 1, 3, 5, 9, 10, 12, 14, 16, 17, and 19. Scores can range from 10-50, with the highest score representing higher levels of positive affect

Analysis: Our canonical analysis will be used on positive affect scores

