### 2.Heart Rate Variability (HRV) during mindfulness meditation

HRV, an index of parasympathetic reactivity, will be obtained during mindfulness meditation alone and during mindfulness meditation with TVS intervention. Increased HRV indicates increased parasympathetic reactivity, which suggests an increased physiological indicator of emotion regulation.

Analysis: Our canonical analysis strategy will be employed on HRV measured during the intervention

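### The SAP's only model for a two-block crossover has no participant, period or order term and names no pre value, so the TVS test is in general not nominal; the main expected harm is lost power

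*SAP*

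**What the plan says.** Protocol section 2.6 describes a within-person design: "Participants will undergo 2 blocks (randomized for order"). The outline adds "Participant will be randomized whether they get meditation first or meditation and TVS first". It gives no allocation ratio or balancing method. Section 2.2 puts everything on one day.

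Both primary outcomes are measured under both conditions. For affect: "The Positive Affect Score will be obtained after mindfulness meditation alone and after mindfulness meditation with TVS intervention". For heart rate variability: "HRV, an index of parasympathetic reactivity, will be obtained during mindfulness meditation alone and during mindfulness meditation with TVS intervention".

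The SAP's Canonical Analysis Strategy supplies the only model: "Pre-intervention index values will be interacted with intervention type (mindfulness alone vs. TVS added to mindfulness) to explain variance in post-intervention index values". If no interaction is found, the post value is first adjusted for the pre value and intervention type is then tested in a residual regression. The effect size is the change in R-squared. Neither step mentions a participant effect, a paired difference, a repeated-measures covariance, a period or an order.

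The pre value is not named for outcomes 1 to 12. Physiology has one labelled baseline, ahead of the first block: "Calibration (EEG, Pupil/Eye tracking, baseline GSR/EKG, vibration"). The affect schedule (PANAS) offers several candidates, since it "will be given initially, and then after each intervention (meditation vs. meditation + TVS"), and "This will also be given after the completion of each task (Mind in the Eyes, Global Local Task").

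**The concern.** A person's two values share that person's level, so the TVS contrast is a within-person contrast. A regression over all rows that ignores this takes its error variance from a mixture of between-person and within-person variation. Its standard error is then right only by coincidence. The word hierarchical does not rescue it: the SAP's moderation strategy adds a third and fourth level of predictors, calls the last one a step, and judges it by change in R-squared. That is block entry of predictors, not a multilevel model with a participant level.

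At stake are the tests of both primary outcomes. The pre-by-type interaction and the moderation tests are also within-person contrasts built on the same model, so they share the fault.

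Outcomes 4 and 5 (Global-Local, Mind in the Eyes) have a further problem. Both tasks are scheduled only after each block, so there is no pre value and the model cannot be fitted to them as written. Outcome 13 has one questionnaire per person and lies outside this point.

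**Working it through.** The plan gives no sample size, power, numeric alpha, SD or correlation, so there is no figure to reproduce. Everything below assumes unit variances and a two-sided 5% test, with equal order groups except in step 5.

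**1. Shared pre value.** Let rb be the correlation of baseline with each block value, and rw the correlation between the two block values.
- The SAP model's row residual variance is 1 − rb².
- The variance that governs the true contrast is 1 − rw, because the shared baseline cancels.
- Reported SE / true SE: f = √[(1 − rb²)/(1 − rw)].
- Actual size = 2[1 − Φ(1.96f)].
- Power when a paired test has 80% = Φ(2.80 − 1.96f).

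| rb = rw | f | SE overstated | Size | Power |
|---|---|---|---|---|
| 0.3 | 1.140 | 14% | 2.5% | 71% |
| 0.5 | 1.225 | 22% | 1.6% | 66% |
| 0.7 | 1.304 | 30% | 1.1% | 60% |

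**2. Shared pre value, correlation decaying by r per step.**
- HRV (calibration, block 1, tasks, block 2): pooled slope b = r(1 + r²)/2 and f = √[(1 − b²)/(1 − r²)]. For r = 0.6, 0.7, 0.8, f = 1.141, 1.195, 1.258 and power is 71%, 68%, 63%.
- Initial PANAS as pre (occasion 0, post scores at occasions 1 and 4): b = (r + r⁴)/2 and f = √[(1 − b²)/(1 − r³)] = 1.052, 1.089, 1.140. Power is 77%, 75%, 71%.

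**3. When the shared-pre test becomes anti-conservative.** f falls below 1 only if rw < rb². With rb = 0.6 and rw = 0.1, 0.2, 0.3, size is 9.8%, 8.0%, 6.1%. To see what that requires, take exchangeable scores with correlation ρ. Let a fraction p of people shift by −d under meditation alone and +d under TVS. The residual covariance becomes ρ − ρ² − d²p(1 − p), which is negative only if d > √[ρ(1 − ρ)/(p(1 − p))]. For ρ of 0.3 to 0.7 and p of 0.2 to 0.5, this is about 0.9 to 1.25 SD in each direction.

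**4. PANAS with the last score before each block as pre.**
- Equal correlations: f = √[(1 + ρ)/(1 + ρ²)] and power = Φ(2.80/√(1 + ρ²) − 1.96f). For ρ = 0.3, 0.5, 0.7, f = 1.092, 1.095, 1.068 and power is 71%, 64%, 58%, against 80% paired.
- Decay: the residual covariance is r³ − r³ − r⁵ + r⁵ = 0, so f = 1. In simulation (40 participants, effect 0.4 SD, r = 0.6, 0.7, 0.8) the SAP test had power of 60%, 69%, 83%. A crossover model using the initial score had 51%, 57%, 70%.

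**5. Omitted period effect, shift of 0.5 SD.** If a share q of participants has one order, the realised bias is 0.5 × |2q − 1|: 0.10 SD at 60:40 and 0.20 SD at 70:30. Over repeated randomization it averages zero. With a shared pre value, equal correlations of 0.3 to 0.7 and simple randomization of 20 to 100 participants (8,000 simulated trials per case), null rejection averaged between about 2% and 4%. It rose above 5% in particular splits:
- 70:30 with 40 participants: 12% to 15%; a split that bad or worse has binomial probability 1.7%.
- 60:40 with 100 participants: 5.9% to 7.7%; probability 5.7%.
- By contrast, 60:40 with 40 participants (probability 27%) gave 2.8% to 4.6%.

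**6. Outcomes 4 and 5.** If the pre term were dropped and rows kept independent, SE overstatement is 1/√(1 − ρ): 20%, 41%, 83% for ρ = 0.3, 0.5, 0.7.

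**The case against.** The SAP never says that rows are independent, and for the two tasks it speaks of comparing the two results with each other, which fits a paired analysis. A competent analyst might pair the data. That is fair as a forecast, but the plan as written directs a different model for every outcome, and the independence assumed above is what that model implies.

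The SAP model also does well in one permitted case: PANAS with the last score before each block and decaying correlation (step 4). This stands, and it means the choice of pre value has a real precision cost either way.

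A reader might infer that the plan inflates false positives. The documents do not support that as the general result:
- Hypothesis 2.2 expects some people to respond in opposite directions, but the shifts needed are large (step 3), and the hypothesis concerns physiology, not PANAS.
- Random order leaves no period bias on average, and the splits that inflate the test are uncommon under simple randomization. Unequal loss of blocks, which Protocol section 2.7 and the SAP's Quality Control allow, could also unbalance the orders; its effect was not simulated.
- Using the score taken straight after block 1 as block 2's pre value would give sizes of 5.8% to 8.4% for equal correlations of 0.3 to 0.7. Nothing in the plan selects that score, and it is not the last one before block 2, since PANAS is repeated after each task.

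**Conclusion.** The concern holds. For outcomes 1 to 12, including both primaries, the stated model ignores the pairing and the period and leaves its pre value open, so the reported standard error and test size of the TVS contrast are in general not nominal. The main expected consequence is lost power: from 80% to about 60% to 71% with a shared pre value and equal correlations of 0.3 to 0.7, and to 63% to 71% for HRV under decay. Anti-conservative behaviour is possible but needs particular conditions. Period bias belongs to the realised split, not to the design on average. These sizes rest on assumed correlations, variances and alpha. The absence of the terms, of a named pre value, and of any pre value for outcomes 4 and 5 does not.

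**What to change.** For outcomes 1 to 12, replace both the interaction step and the residual-regression step with one crossover mixed model:
- One row per participant and period, with fixed effects for intervention type, period and sequence.
- An unstructured 2×2 within-participant covariance. Do not substitute a random intercept bounded at zero: in the step 3 cases it still rejected 9.2%, 7.9% and 5.9% of nulls, against 4.7% to 4.9% with the unrestricted covariance. Nor is a random intercept generally equivalent when variances differ or blocks are lost.
- A named pre value, taken before block 1 (calibration for physiology, initial score for PANAS) and mean-centred. Keep the pre-by-intervention term, so that the TVS effect is read at the mean pre value.
- For PANAS, a sensitivity analysis with the score just before each block. State that it may be appreciably more precise if correlation decays, but that the second such score follows the first block's treatment.
- No pre terms for outcomes 4 and 5.
- Moderator-by-intervention-type interactions, named as such, tested in the same model.
- A statement that both blocks fall on one day and that a sequence term does not remove carry-over.

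Exclude outcome 13. The cost is SAP rewording, including the moderation steps, and slightly more analysis work. No new data are needed.

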1.2 Specific Aims

Aim 1: Examine how TVS added to brief instructed mindfulness meditation can affect psychological state and performance. This aim is to show that TVS is particularly potent as a catalyst towards the types of experiences documented in experienced meditators.

Hypothesis 1.1: Positive affect and calmness: TVS added to mindfulness will increase subjective positive affect and calmness compared with mindfulness alone, particularly in individuals whose state is not strongly affected by mindfulness alone.

Hypothesis 1.2: Heightened states of awareness: TVS added to mindfulness will heighten state of awareness compared with mindfulness alone and particularly in individuals whose state is not strongly affected by mindfulness alone.

Hypothesis 1.3: Performance: TVS added to mindfulness will improve performance on visual attentional preference and empathy tasks and particularly in individuals whose state is not strongly affected by mindfulness alone and in individuals with increased positive affect and heightened state of awareness.

Aim 2: Examine how TVS added to brief instructed mindfulness meditation can affect physiological indicators of emotion regulation. Our overall hypothesis is that TVS, in combination with some other task, increases performance on that task by increasing emotion regulation. Mindfulness meditation is one such task that, without TVS may decrease emotion regulation in some people - TVS will counter that.

Hypothesis 2.1: TVS added to mindfulness increases physiological indicators of emotion regulation, including decreased galvanic skin response (GSR; index of sympathetic reactivity), increased heart rate variability (HRV; index of parasympathetic reactivity), and increased prefrontal gamma and theta band EEG compared with mindfulness alone during the intervention and follow-up tasks.

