### Other Pre-specified Outcome Measures: Moderation Analyses

#### **Canonical Moderation Analysis Strategy**

Moderation analyses will be analyzed by adding a third and fourth level to the hierarchical regressions described in our Canonical Analysis Strategy. On the third level, moderating variables are added. On the fourth level interactions of the moderating variables with primary and secondary outcome variables will be added. The change in R^2 from the third to the fourth level will be used as an effect size, and the significance of adding the interaction term on the fourth step will be interpreted as the significance of the moderation effect. Statistically significant moderation effects will be followed with creation of level curves for the 25th, 50th, and 75th percentiles for relevant variables to understand simple effects of the moderator on primary and secondary outcomes.

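### The plan tests TVS against mindfulness alone only if a preliminary interaction test is negative, so a positive one leaves both primary outcomes with no named treatment result

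*SAP*

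**What the plan says.** The Analysis paragraph of the SAP's Canonical Analysis Strategy has two steps. The first is an interaction, fitted by hierarchical regression: "Pre-intervention index values will be interacted with intervention type (mindfulness alone vs. TVS added to mindfulness) to explain variance in post-intervention index values". The second is the comparison of the two conditions, under a condition: "in the absence of an interaction, preintervention values will be regressed from post-intervention values before using intervention type as an independent variable". The effect size is the change in R². The paragraph has no sentence for the case where an interaction is found, and no significance level for deciding that it is absent.

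Both primary outcomes refer back to this paragraph and add no rule of their own. For positive affect: "Our canonical analysis will be used on positive affect scores". For heart rate variability (HRV): "Our canonical analysis strategy will be employed on HRV measured during the intervention".

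The Canonical Moderation Analysis Strategy works by "adding a third and fourth level to the hierarchical regressions described in our Canonical Analysis Strategy", and there "the significance of adding the interaction term on the fourth step will be interpreted as the significance of the moderation effect". Its percentile curves follow significant effects of the moderators in items 14 to 16.

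In Protocol section 1.2, Hypothesis 1.1 states what the added stimulation is expected to do: it "will increase subjective positive affect and calmness compared with mindfulness alone, particularly in individuals whose state is not strongly affected by mindfulness alone". Hypothesis 2.1 says that "TVS added to mindfulness increases physiological indicators of emotion regulation", again relative to mindfulness alone. Under Protocol section 2.6, every participant goes through both blocks in randomised order.

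**The concern.** The hypotheses behind the two primary outcomes are contrasts between conditions. As written, a preliminary test on the same data can decide whether that contrast is produced. If the interaction is significant, the analyst has to choose the headline result after seeing the data. A significant interaction is informative, since it shows that TVS matters at some baseline values. It does not replace the average contrast, and a change in R² has no sign, so it cannot show an increase.

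Hypothesis 1.1 expects a larger effect in some people, so effect modification is foreseen. The modifier it names is response to mindfulness, not the pre-intervention value, so the preliminary test does not examine that clause either.

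Two further gaps affect what the preliminary test would be:

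- **Pairing.** The SAP does not say whether each person's two blocks are analysed as a pair.
- **Baseline.** It does not say which reading is the pre-intervention value. Protocol section 2.5 gives the affect scale at the start, after each intervention and after each task. Under section 2.6, the baseline EKG comes from calibration, before both blocks.

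**Working it through.** **Step 1: what each branch yields.** The documents state no sample size, alpha, power or effect, so there is no figure of the plan's own to reproduce.

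| Interaction | Comparison of conditions described in the SAP |
|---|---|
| Absent | Residual regression on intervention type |
| Present | None named |

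The percentile curves do not fill the second row. They belong to the third and fourth regression levels and to the moderators in items 14 to 16. Those added levels imply that two earlier ones exist, and an intervention term may sit on one of them. The SAP neither lists these levels nor calls such a term the primary result.

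**Step 2: illustration of size. All inputs are assumed.** One baseline z per person (SD 1), baseline coefficient 0.5, TVS effect 0.45, residual SD 1, within-person correlation 0.5, two-sided alpha 0.05:

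Y = 0.5z + TVS × (0.45 + slope × z) + e

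- *Paired:* a period effect of 0.2 is added, and the within-person difference is regressed on sequence sign and centred z. The preliminary test is the z slope; the treatment test is the intercept.
- *Unpaired:* two rows per person, with no participant or period term. The preliminary test is the product term; the treatment test is the residual regression.
- *Conditional rule, worst reading:* every significant interaction counts as no treatment result.

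Simulated with 40,000 runs per setting (%):

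| Analysis | N | Slope | Interaction significant | Treatment significant, always tested | Treatment significant, conditional rule |
|---|---|---|---|---|---|
| Paired | 40 | 0 | 5.0 | 79.2 | 75.1 |
| Paired | 40 | -0.2 | 23.0 | 78.8 | 60.3 |
| Paired | 40 | -0.4 | 65.8 | 77.4 | 26.0 |
| Unpaired | 40 | 0 | 0.7 | 52.8 | 52.4 |
| Unpaired | 40 | -0.2 | 7.0 | 52.0 | 48.2 |
| Unpaired | 40 | -0.4 | 38.2 | 50.3 | 31.0 |
| Paired | 20 | -0.2 | 12.6 | 48.0 | 41.1 |
| Paired | 80 | -0.2 | 41.6 | 97.6 | 56.8 |
| Unpaired | 20 | -0.2 | 3.2 | 23.7 | 22.8 |
| Unpaired | 80 | -0.2 | 16.1 | 88.4 | 74.1 |

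**Step 3: hand check of the paired N=40, slope -0.2 row.**

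- SD of a within-person difference = √(2 × (1 − 0.5)) = 1, so SE = 1/√40 = 0.158.
- Treatment: 0.45/0.158 = 2.85. The critical t on 37 df is 2.03. Power ≈ Φ(0.82) = 0.79.
- Interaction: 0.2/0.158 = 1.26. Power ≈ Φ(1.26 − 2.03) = 0.22.
- Conditional rule ≈ 0.788 × (1 − 0.230) = 0.61, against 0.603 simulated.

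**Step 4: sensitivity to the correlation** (N=40, slope -0.2, always tested v conditional). With correlation 0.3: paired 65.0% v 53.2%, unpaired 51.7% v 46.5%. With 0.7: paired 94.2% v 61.5%, unpaired 52.8% v 50.9%.

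**Step 5: the opposite reading.** Suppose either a significant interaction or a significant main effect may be claimed as the TVS finding, each at 0.05. For independent tests, the false-positive rate with no effect at all is 1 − 0.95² = 9.75%. Paired simulation (4,000 runs per setting) gives 8.8% to 9.6% for N of 20, 40 and 80.

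**The case against.** The strongest reply is that hierarchical regression normally enters lower-order terms before their product, and the SAP's own moderation section follows that pattern. An intervention term would then be fitted before any interaction is examined, and if it is reported nothing is lost. This stands as a plausible reading. However, the first two levels are never listed. If baseline and intervention enter together, their change in R² does not isolate TVS.

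Second, counting every significant interaction as no result is the worst reading. The two events are disjoint, so in the paired N=40 case either an interaction or a conditional main effect is significant in 23.0 + 60.3 = 83.3% of trials at slope -0.2 (78.8% if the treatment is always tested), and in 65.8 + 26.0 = 91.8% at -0.4 (77.4%). That is correct, but it exchanges lost power for the false-positive rate of nearly 10% in step 5. The SAP promises Type I error control across the factors examined but states no split between these two tests.

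Third, the largest losses need a paired model, which the SAP does not describe, together with a steep slope. Unpaired at N=40, the losses are 0.4, 3.8 and 19.3 points for slopes 0, -0.2 and -0.4. This stands: the documents support no particular size of loss.

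Finally, checking for equal slopes before a common-slope covariance analysis is familiar practice, and preferring the average effect is partly a choice of estimand. Here the hypotheses have already made that choice.

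**Conclusion.** The concern holds. The SAP states a conditional testing rule that can withhold the contrast its primary hypotheses are about, and no other text supplies a result for the missing branch. This rests on the wording and not on the simulation.

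The size depends on how the plan is read. It is zero if an earlier-level intervention term is always reported. On the worst reading with 40 participants, it runs from under 1 point (unpaired, no interaction) to about 51 points (paired, slope -0.4: 77.4 − 26.0). Sample size, alpha, effect, slope and correlation are all assumed.

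This should be corrected before analysis. Confidence is medium, because the authors may have intended an earlier-level term and not written it down.

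**What to change.** For each primary outcome, state in the SAP that the average TVS effect is estimated and tested whether or not an interaction is found, from one paired model of the two blocks:

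- **Terms:** participant, intervention type, period (first or second block), and intervention type × mean-centred pre-intervention value.
- **Participant random:** add the baseline main effect. This keeps people with one usable block, which Protocol section 2.7 and the SAP's Quality Control rule make likely. If 6 of 40 have one block (correlation 0.5, taken as known), the SE of the treatment effect is 0.168, against 0.171 with participant fixed.
- **Participant fixed:** omit the baseline main effect and sequence. With one baseline per person they are aliased with participant; in a check with 20 participants, adding both left the design rank at 20.
- **Baseline:** name the pre-intervention value. The initial affect score and the calibration EKG both come before either block.
- **Interaction:** report the product term as moderation that never decides whether the treatment test is run.
- **Two-step residual regression:** drop it. With complete data and one shared baseline it gives the same treatment estimate as the joint model.
- **Alpha:** state the level.

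The cost is SAP wording and no new data. The period and product terms use one degree of freedom each. Always running the paired test keeps its false-positive rate at 5.1% (simulated, N=40, nominal 5%).
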